**Comparison Between Gastric and Post Pyloric Tube Feedings in Bronchiolitis Patients
Requiring High Flow Nasal Cannula**

NCT03346850

Version Date: 03/26/2018

Protocol Title:	Comparison Between Gastric and Post Pyloric Tube Feedings in Bronchiolitis Patients Requiring High Flow Nasal Cannula
Principal Investigator:	[name]
Co-Investigators:	[name], [name], [name], [name], [name], [name], [name], [name]
Population:	All children less than 12 months old admitted to Children's Memorial Hermann Hospital TMC for bronchiolitis requiring high flow nasal cannula therapy
Number of Sites:	Single site – Children's Memorial Hermann TMC
Study Duration:	Continuous enrollment until sample size reached
Subject Duration:	Duration of acute hospitalization

General Information

- There are no clear guidelines on appropriate route for nutrition in infants with bronchiolitis, especially during the use of high flow nasal cannula (HFNC). Enteral feed nutrition is achieved by nasogastric (NGT) and nasoduodenal tube (NDT) in general or intravenous hydration (IVF) until the infant's respiratory status improves. This practice varies between hospitals and evidences are anecdotal. We will compare gastric versus post pyloric tube feedings in children less than 12 months old admitted for bronchiolitis requiring high flow nasal cannula therapy

Background Information

- Bronchiolitis is the most common cause of hospitalization among infants during the first 12 months of life. HFNC is becoming increasingly common in supportive care for these patients. No randomized control trials currently exist regarding the safety of tube nutrition in patients receiving HFNC.
- The purpose of NDT feeds is to prevent gastric reflux and subsequent airway aspiration. However, NDT feedings are more difficult to place and less physiologic than gastric feedings. High flow nasal cannula provides humidified air at flows that provide a variable amount of positive pressure. There are cohort studies in adults with Continuous Positive Airway Pressure (CPAP) that show that increased positive pressure can create a decreased esophageal sphincter tone and increased incidences of gastroesophageal reflux. It is unclear if a similar mechanism exists for HFNC therapy.
- Our hypothesis is that NGT is well tolerated during HFNC without serious adverse events. We hypothesize that there will be no difference in length of HFNC therapy, number of emesis, peak respiratory support between patients receiving NGT compared to NDT. We also hypothesize that there will be no difference in these outcomes in the subgroup of high risk population: premature infants, neurological disorders, gastroesophageal reflux patients.

Objectives

- The primary objective is to compare length of respiratory support, number of emesis documented by nursing, peak respiratory support (flow of HFNC, or y/n on CPAP/MV), and ER revisit/hospitalization rates between the gastric feeding group and the post pyloric feeding group

- The secondary objective is to perform an analysis of the highest risk population: premature (born < 37 weeks gestation), neuromuscular disorders, seizures, cerebral palsy, EOE, upper airway disorders – laryngo/tracheomalacia, hemodynamically unstable heart disease, medically managed GERD; and compare the same outcomes between NGT and NDT feedings in this group compared to the low risk group (>37 weeks gestation with none of the above comorbidities).

Study Design

- Design will be a randomized controlled trial.
- Stratified Block Randomization will be done for both high risk population and low risk population through REDCap.
- Duration of study will be until calculated sample size is reached. Subjects will be followed during their acute hospitalization and then followed up by phone interview 7 days and 30 days after discharge
- The primary outcome is total length respiratory support. If HFNC causes increased rates of reflux and subsequent aspiration, we expect length of therapy to be increased in NGT group compared to the NDT group.
- Our secondary outcomes include number of emesis, peak respiratory support, number of x-rays obtained, length of stay, and ER revisit and hospital readmission rates.
- Safety assessments by clinicians will be done daily by primary physician based off of standardized criteria of number of emesis in conjunction with need for increased respiratory support to determine if feeds should be held or not. Patients that transferred to the PICU will be an outcome we track however this study will not dictate ICU feeding management.
- No blinding for study authors involved as they are attending physicians caring for the infants
- Data will be blinded for the statistician and the investigator making follow up phone calls

Study Population

- Inclusion criteria: All admitted patients less than 12 months old for bronchiolitis requiring high flow nasal cannula therapy at Children's Memorial Hermann.
- Exclusion criteria: Patients with craniofacial abnormalities that prevent tube placement. Patients with prior surgery compromising esophageal sphincter tone such as Nissen fundoplication or congenital hiatal hernia surgery are excluded. Patients requiring CPAP and mechanical ventilation are also excluded from the study.
- Recruitment strategy: When patients are either started on HFNC on the inpatient floor or transferred from the emergency room on HFNC without enteral nutrition, caretakers will be asked to consent to the study by the study investigators when the primary physicians have made the clinical decision to start tube feedings.

Study Procedures

- Once consented, patients will be randomized into a NGT or NDT group – via stratified block randomization module on UTH REDCap
- Chest X-ray will be obtained to confirm placement of tube before feeding is initiated
- Feeds will be initiated in a standardized rate and volume
- Patients will be continued to be fed according to randomization until HFNC is discontinued.
- Caretakers can withdraw patients from study at any point
- Primary physicians can withdraw patient from study at any point if they are concerned about adverse events

- Bronchiolitis and HFNC will be managed per standard bronchiolitis protocol
- Continued admission and subsequent discharge will be determined by primary physician
- Information to be gathered includes demographic information (age, sex, race, weight), historical information (birth history, past medical, family history), and information about the course of the admission (length of stay, number of emesis, number of x rays performed, antibiotics used, peak respiratory support, number of revisits to ER and rehospitalizations)
- Data will be collected through chart review in EMR as well as phone follow up interview 7 days and 30 days after discharge by blinded investigators

Data and Safety Monitoring

- Adverse events including reflux and subsequent aspiration are theoretically possible and the purpose of this study. There have been several studies involving nutrition in bronchiolitis that have shown NGT feedings to be safe (3,4,5). If the clinician believes that aspiration/reflux is the cause of worsening respiratory distress and respiratory support, the mode of feeding can be changed if deemed necessary by treating physician.
- A review will be conducted by the safety coordinator of the research team at the 50% enrollment mark. Because this is a randomized control trial with equal groups, a standardized normal deviate test as described in <https://www.ncbi.nlm.nih.gov/pmc/articles/PMC1471979/> will be calculated at this time. The cumulative results of adverse events will be used with $p < 0.05$ as the level of significance. If it is shown that there is increased aspiration and this arm is not safe, the trial and study will end.

Statistics

- Statistical analysis will be performed by UT Houston statistician or through CCTS
- Based on retrospective data of bronchiolitis admissions over the past 3 years, the average length of HFNC for low risk infants were 83.3 hours with a standard deviation of 29.5. The average length of HFNC for high risk infants were 87.75 with a standard deviation of 40.06. Assuming B of 0.8 and alpha of 0.05, an N of 48 and 88 were calculated to detect a difference of 24 hours in the duration of HFNC in the low and high risk group respectively.
- $p < 0.05$ to be used for level of significance
- All randomized subjects will be included in the analysis. Subsequent subgroup analysis will be performed on gestational age at birth, weight at study entry, birth weight, mode of delivery PMH by organ system, viral organism, and level of respiratory support.
- In the case that the calculated sample size is not reached by the end of the second respiratory season, enrollment will continue until Bayesian analysis performed annually for up to 2 years identifies 90% or greater probability that there is a difference of respiratory support duration between the two groups or until planned sample size is met.

Statistical Analysis Plan

All analyses will be intent-to-treat. Differences in length of HFNC therapy between treatment groups will be assessed with a regression model including treatment and risk group (stratifying variable) as covariates. Rates of secondary outcomes will be assessed using log binomial or logistic models, and total number of secondary outcomes will be assessed with negative binomial models. In this small pilot study, some treatment effects that would be considered important by family members and clinicians (reduced hospital days) may not be statistically significant. As a result, Bayesian analyses will also be performed to estimate the probability of benefit. Neutral, weakly informative priors will

be used for the treatment effect, e.g. for binary outcomes, the prior relative risk will be centered at 1.0 with 95% prior interval of 0.5-2.0.

Ethics

- IRB approval will be sought from CPHS
- Consent will be obtained prior to any enrollment into the trial.
- A consent form will be printed and handed to each patient describing the purpose of the trial and the risks involved

Data handling and record keeping

- Data will be stored on UTShare account and requiring 2 step authentication and PHI protected as well as the UT Houston REDCap.
- There will be no paper records
- Data will be kept until ten years after completion of study

Quality control and assurance

- Self assessments will be made to check that data collected were for patients admitted for bronchiolitis and the other inclusion criteria

Publication Plan

- Dissemination of knowledge from this study by resident education, nursing education, abstract and poster presentation leading to medical journal publication

CITATIONS

2. Shepherd, Kelly, David Hillman, and Peter Eastwood. "Symptoms of Aerophagia Are Common in Patients on Continuous Positive Airway Pressure Therapy and Are Related to the Presence of Nighttime Gastroesophageal Reflux." *Journal of Clinical Sleep Medicine* (2013)

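### The primary outcome has no stated time zero and most naturally includes HFNC hours before randomisation, which the primary regression does not adjust for: a forgone gain in precision that one covariate would recover.

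*Combined protocol and SAP*

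**What the plan says.** Study Design: "The primary outcome is total length respiratory support". The Statistical Analysis Plan names the analysed quantity a little differently: "Differences in length of HFNC therapy between treatment groups will be assessed with a regression model", the model "including treatment and risk group (stratifying variable) as covariates". Neither section says at what moment the duration begins.

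The recruitment strategy under Study Population fixes the order of events. Families are approached "When patients are either started on HFNC on the inpatient floor or transferred from the emergency room on HFNC without enteral nutrition", and consent is sought "when the primary physicians have made the clinical decision to start tube feedings". Study Procedures then states "Once consented, patients will be randomized into a NGT or NDT group", followed by "Chest X-ray will be obtained to confirm placement of tube before feeding is initiated". So HFNC start comes first. The decision to tube feed, consent, randomisation, X-ray confirmation of the tube and the assigned feeding come after it.

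The Statistics section takes its planning figures from retrospective HFNC lengths: mean 83.3 h, SD 29.5 (low risk) and mean 87.75, SD 40.06 (high risk; hours presumed). From these it derives N = 48 and N = 88 for a 24 h difference. The data items listed under Study Procedures do not include HFNC start time or the interval from HFNC start to randomisation.

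**The concern.** Hours on HFNC before randomisation cannot respond to gastric versus post-pyloric feeding. Their number will differ between infants, because it depends on where HFNC began and on when the physician decides to feed by tube. If the outcome counts them, that variation enters the comparison, and a model with only treatment and risk group cannot remove it. At stake is the width of the interval around the treatment difference in a study that the SAP itself calls a small pilot. The missing time zero is a gap in its own right, because two analysts could compute different primary outcomes from the same chart.

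**Working it through.** **Inputs.** From the Statistics section: SD of HFNC length 29.5 h (low risk) and 40.06 h (high risk); difference 24 h; power 0.80 (written there as a B of 0.8); alpha 0.05, sidedness not stated. Equal groups come from Data and Safety Monitoring. Not in the documents, so assumed: the SD of HFNC hours before randomisation (SD_pre), and the correlation rho between hours before and after randomisation.

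**1. The plan's own figure.** n per arm = 2 × (1.960 + 0.842)² × SD² / 24².
- Low risk: 15.70 × 870.25 / 576 = 23.7, so 24 per arm, N = 48.
- High risk: 15.70 × 1604.80 / 576 = 43.7, so 44 per arm, N = 88.

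Both reproduce exactly, two-sided (one-sided would give 38 and 70). The t-based versions are 50 and 90, with power at 48 and 88 of 0.788 and 0.794. The SDs describe whole HFNC courses from admissions with no randomisation point, so the stated N already carries any variation in the early hours.

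**2. Gain under independence (rho = 0).** Share of variance = SD_pre² / SD_total². Reduction in standard error = 1 − √(1 − share).

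| SD_pre (h) | Share, low | SE reduction, low | Share, high | SE reduction, high |
|---|---|---|---|---|
| 8 | 64/870.25 = 7% | 4% | 64/1604.80 = 4% | 2% |
| 12 | 144/870.25 = 17% | 9% | 144/1604.80 = 9% | 5% |
| 16 | 256/870.25 = 29% | 16% | 256/1604.80 = 16% | 8% |

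**3. Other correlations, SD_pre = 12 h.** Solve SD_total² = SD_pre² + SD_post² + 2 × rho × SD_pre × SD_post for SD_post. Moving time zero alone leaves SD_post as the error. Adding the covariate leaves SD_post × √(1 − rho²). Power is two-sided, t-based, at the planned 48 and 88, and ignores the single degree of freedom spent on the covariate.

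| rho | Time zero moved only: SD low / high | Power | With covariate: SD low / high | Power |
|---|---|---|---|---|
| +0.3 | 23.6 / 34.8 | 0.932 / 0.892 | 22.5 / 33.2 | 0.951 / 0.918 |
| 0 | 26.9 / 38.2 | 0.855 / 0.830 | 26.9 / 38.2 | 0.855 / 0.830 |
| −0.3 | 30.8 / 42.0 | 0.753 / 0.755 | 29.4 / 40.1 | 0.791 / 0.794 |
| −0.5 | 33.6 / 44.7 | 0.678 / 0.702 | 29.1 / 38.7 | 0.799 / 0.820 |

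Moving time zero alone breaks even at rho = −SD_pre / (2 × SD_post). At that point SD_post equals SD_total, so rho = −12/59 = −0.20 (low) and −12/80.12 = −0.15 (high). Below those values it loses precision.

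**4. Why the covariate does not depend on rho.** The variance of the total can be written as (SD_pre + rho × SD_post)² + SD_post² × (1 − rho²). The second term is the residual variance after adjustment. The first cannot be negative, so the residual SD never exceeds the SD of the total. Also, total = before + after. With the earlier hours in a linear model, changing the outcome from one to the other shifts only the coefficient on those hours, by exactly 1. The treatment estimate and its standard error are the same.

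**5. Size of chance imbalance, SD_pre = 12 h.** With 68 infants per arm, the SE of the difference in mean earlier hours is 12 × √(2/68) = 2.1 h, a 95% range of about ±4.0 h against the 24 h target. Within strata it is about ±6.8 h (24 per arm) and ±5.0 h (44 per arm).

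**The case against.** The strongest reply is that nothing planned is lost. The sample size was built on the SD of the whole HFNC course, so the early variation is already paid for. The regression also pools the strata. With 136 infants, the pooled SD is √((48 × 870.25 + 88 × 1604.80)/136) = 36.7 h and the SE is 36.7 × √(2/68) = 6.3 h. That gives about 97% power for 24 h by the normal approximation. This stands: the point concerns efficiency forgone, not a shortfall against the plan.

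A second reply is that no section actually says the early hours are counted. The word total could mean summed over modes of support, since CPAP and mechanical ventilation are tracked as outcomes. That is possible. Counting from HFNC start remains the likelier reading because the planning data are whole HFNC lengths, but it is an inference, and the documented fact is an undefined time zero.

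Three stronger readings are tempting, and the documents do not support them.
- A reader might infer that counting the early hours must add noise. If illness runs a roughly fixed course, infants randomised later have less time left, rho is negative, and the total can vary less than the time from randomisation.
- A reader might infer that imbalance in those hours biases the result. Under randomisation it is chance imbalance, already reflected in the standard error.
- A reader might infer that the extra variance favours the hypothesised finding of no difference. Given the planned power, that carries little weight at 24 h.

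**Conclusion.** The concern holds as a cheap improvement. Randomisation follows HFNC start in every infant, time zero is not defined, and the primary model leaves variation in the earlier hours unadjusted. At an assumed SD_pre of 12 h, adjustment takes the residual SD from 29.5 to between 22.5 and 29.4 h (low risk), and from 40.06 to between 33.2 and, to rounding, no change (high risk), for rho from +0.3 to −0.5. Both SD_pre and rho are assumptions; the documents give neither, so no single figure for the gain can be stated. The unadjusted comparison remains valid.

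**What to change.** 1. In Study Design, define the primary outcome as hours of respiratory support from randomisation, and use the same definition in the Statistical Analysis Plan and in the Bayesian continuation rule in Statistics.
2. Add to the data items the HFNC start time (from the chart) and the randomisation time (from REDCap), and derive the HFNC hours between them.
3. Add those hours as a covariate in the primary regression, beside treatment and risk group. This is the step that protects precision; step 1 should not be adopted without it.
4. Keep total length as a descriptive outcome.

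The cost is one chart field, one model term and one error degree of freedom. HFNC start has to be extracted in any case to compute total length. The documents do not say that a randomisation time is stored, so this should be confirmed. The Statistics section needs a note that the planning SDs describe whole HFNC length; N of 48 and 88 can stand.

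### The single between-arm safety review is triggered only by 50% enrollment; with slow accrual, or an early stop on duration, it can come late or not at all

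*Combined protocol and SAP*

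**What the plan says.** The Data and Safety Monitoring section sets the timing of the comparative review: "A review will be conducted by the safety coordinator of the research team at the 50% enrollment mark". Its input is stated as "The cumulative results of adverse events will be used", with a normal deviate test at p < 0.05. Its consequence is "If it is shown that there is increased aspiration and this arm is not safe, the trial and study will end". No earlier, later, calendar-based or event-count trigger appears in the document.

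The Statistics section gives the sample size ("an N of 48 and 88 were calculated to detect a difference of 24 hours in the duration of HFNC", for the low and high risk strata respectively) and a rule for slow recruitment. It begins "In the case that the calculated sample size is not reached by the end of the second respiratory season" and continues "enrollment will continue until Bayesian analysis performed annually for up to 2 years identifies 90% or greater probability" of a difference in respiratory support duration, or until the planned size is met. The rule names no direction for the difference and does not mention adverse events or the safety review.

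Other safety provisions concern individual infants: daily assessment by the primary physician (Study Design), withdrawal by the physician (Study Procedures) and a change of feeding mode (Data and Safety Monitoring).

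**The concern.** The plan describes reflux and aspiration as possible adverse events and as the reason for doing the study, and it provides a between-arm test with a stopping consequence. That test is tied to a headcount. The same plan allows for recruitment slow enough to miss the full sample after two seasons, and in that case it opens the data by arm each year for duration only.

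Followed as written, the rule that compares adverse events between arms may therefore operate only after two full seasons, or never, while by-arm data are being analysed for another purpose. The participants are infants under 12 months, and 88 of the planned 136 are in the high risk stratum.

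**Working it through.** **1. Where the 50% mark falls.** Inputs from the Statistics section: SD 29.5 h (low risk) and 40.06 h (high risk), difference 24 h, and "Assuming B of 0.8 and alpha of 0.05", read as 80% power and two-sided 0.05. Per arm, n = 2 × [SD × (1.960 + 0.842) / 24]².
- Low risk: 23.7, rounded up to 24 per arm, 48 in total.
- High risk: 43.7, rounded up to 44 per arm, 88 in total.

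Both stated figures reproduce. (One-sided testing would give 38 and 70, so two-sided was used.) The pooled total is 136 and half is 68, or 34 per arm. The plan does not say whether 50% is pooled or per stratum. If per stratum, the marks are 24 and 44 infants, and the slower stratum could be reviewed later still.

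**2. When infant 68 is enrolled.** Assumptions: constant accrual of r infants per season, one season per year, and an extension of two seasons after season 2, so four in all. Infant 68 arrives after 68/r seasons.

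| Infants per season | Enrolled after 2 seasons | Review falls |
|---|---|---|
| 68 or more | 136 or more | by the end of season 1; extension not used |
| 34 to 67 | 68 to 134 | within two seasons; extension used |
| 17 to 33 | 34 to 66 | season 3 or 4 (33: 2.1 seasons; 25: 2.7; 20: 3.4; 17: 4.0) |
| below 17 | below 34 | not within four seasons (16: 64 infants, 47%; 10: 40 infants, 29%) |

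**3. Skipping the review through a duration stop.** Take a look at 60 infants, 30 per arm. Assumptions: strata in planned proportions, the plan's HFNC SDs standing in for respiratory support, a flat prior, and the rule met when the posterior probability of a difference in one direction or the other is at least 90%.
- Pooled SD = √[(48 × 29.5² + 88 × 40.06²) / 136] = 36.7 h.
- SE = 36.7 × √(2/30) = 9.5 h.
- The rule is met when |difference| / SE ≥ 1.28.
- Probability of meeting it at that one look: about 20% with no true difference, 50% with 12 h and 89% with 24 h.

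The plan does not date the first annual look. If it is at the end of season 2, 60 infants corresponds to 30 per season. If it is a year later, 60 corresponds to 20 per season; in that case a look before infant 68 needs 22 or fewer per season (3 × 22 = 66; 3 × 23 = 69).

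**4. What a review at that point could do.** The documents give no aspiration rate, so these are assumptions. With a pooled z test, |z| > 1.96, harm direction, a trial that ends at 60 infants has a 0% chance of the harm rule acting as written. One look at 30 per arm would act in about 45% of trials at 20% vs 5%, and in about 10% at 10% vs 5%.

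**5. Price of more looks.** At 30 per season, looks at the end of season 2 and at the two annual cuts fall at 30, 45 and 60 per arm. With equal true rates and unadjusted p < 0.05, harm-direction false stops are:

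| Event rate, both arms | One look, 34 per arm | Looks at 30, 45, 60 per arm |
|---|---|---|
| 5% | 1.7% | about 4% |
| 10% | 2.8% | 5.3% |

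If an excess in either arm can stop the trial, these figures double. The plan leaves this open, since it gives neither the sidedness of the test nor the arm meant.

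**The case against.** A reader might infer that the plan expects its safety review to be late. It does not. The slow-recruitment clause concerns missing 136, not missing 68; at 34 to 67 infants per season the clause applies and the review still falls within two seasons. Lateness needs less than half the pace that would fill the trial in two seasons, and no accrual rate is given. That limits the point to a possibility, but one the plan's own rules allow.

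A reader might also infer that infants are unmonitored or that the annual looks have no bearing on safety. Neither is so. The bedside provisions protect individual infants, and Study Design expects aspiration to lengthen therapy in the gastric arm, so duration is an indirect marker of harm. But bedside decisions cannot show an excess in one arm, and the annual criterion has no direction and counts no adverse events. The Bayesian models for binary outcomes in the Statistical Analysis Plan are not tied to the annual looks.

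A large gain in detection is also tempting to claim: at 20% vs 5%, one look at 34 per arm stops about 50% of trials and looks at 20, 34 and 50 per arm about 71%. That comparison rests on assumed rates and includes a look at 100 infants, so it does not measure the effect of a missing review.

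Finally, a single mid-trial review is a legitimate choice for a study the plan calls a small pilot. The lack of a further review for the second 68 infants is not in itself an error.

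**Conclusion.** The point holds in a conditional form. A stated stopping rule can fail to operate under the plan's own provisions, because its only trigger is a headcount and the trial can run on, or end on duration, without reaching it. Under constant accrual over an assumed four seasons, the review is late at 17 to 33 infants per season and absent below 17. Slow accrual combined with a duration stop before infant 68 also removes it; a look at 60 infants would meet the duration rule in about 20% to 89% of trials for true differences from 0 to 24 h. These figures rest on the assumed accrual pattern, the pooled reading of 50%, the flat prior (a more sceptical prior would lower them) and the either-direction reading of the 90% rule. The documents do not show that the review will be missed.

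**What to change.** Amend Data and Safety Monitoring so that:
- the between-arm safety review is held at 50% enrollment or at the end of the second respiratory season, whichever comes first;
- adverse events by arm are reviewed on the same data cut as each annual Bayesian analysis, before any duration-based decision to stop or continue;
- the text says whether 50% is pooled or per stratum, and whether an excess in either arm or only one named arm can stop the trial.

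The cost is a few sentences of protocol text and one event table by arm at each review, prepared for the same safety coordinator; the annual cuts are already being made. The statistical cost is the rise in false safety stops shown above, roughly 2.5 percentage points in the harm direction in the 30/45/60 example and twice that if either arm can trigger a stop. The plan should either state that figure and accept it, or split the 0.05 across the looks (for three equal shares, 0.05/3 = 0.017 each), which lowers the chance of detecting real harm at each look.

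### The 50% safety test names no risk-group term although randomisation and the primary model do; if it is a pooled two-proportion test, it can lose some power for harm when event rates differ widely between strata

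*Combined protocol and SAP*

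**What the plan says.** Under Study Design, risk group is the stratifying factor: "Stratified Block Randomization will be done for both high risk population and low risk population through REDCap". The Statistical Analysis Plan carries it into the primary comparison of HFNC duration through "a regression model including treatment and risk group (stratifying variable) as covariates".

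Data and Safety Monitoring sets the only between-arm safety test: "A review will be conducted by the safety coordinator of the research team at the 50% enrollment mark". The method is introduced with "Because this is a randomized control trial with equal groups, a standardized normal deviate test" and is otherwise defined by a web link. The data are cumulative adverse events and the level is 0.05, with no statement of whether it is one- or two-sided. The consequence is stated: "If it is shown that there is increased aspiration and this arm is not safe, the trial and study will end". Risk group does not appear anywhere in that section. The documents give no adverse-event rate, overall or by stratum, and no power for this test.

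**The concern.** The feared event is reflux with aspiration. The high-risk stratum is defined partly by medically managed reflux disease, neuromuscular disorders, cerebral palsy and upper airway disorders, so a higher event rate there is plausible. The plan also has a separate hypothesis for these infants.

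Stratified block randomisation balances the arms within each stratum. The difference in event counts between arms then varies only with the within-stratum variances. A pooled two-proportion test divides by a variance that also contains the difference in risk between strata. When that difference is large, the denominator is too big and the test rejects too seldom. Here the affected test is the one that can end the trial for harm, so lost power means continued exposure. Pooled totals also do not show whether excess events sit in the high-risk infants.

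**Working it through.** **Inputs from the documents (Statistics section).** Low risk: "the average length of HFNC for low risk infants were 83.3 hours with a standard deviation of 29.5". High risk: mean 87.75 h, SD 40.06. Difference 24 h, alpha 0.05, power 0.80 (written as B), N of 48 and 88.

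**The plan's own figures first.** Per arm, n = 2·SD²·(1.960 + 0.842)² / 24², two-sided.
- Low risk: 23.7, so 24 per arm and 48 in total.
- High risk: 43.7, so 44 per arm and 88 in total.

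Both reproduce, and they confirm a two-sided 0.05 for the sample size.

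**Assumptions for the safety test.** The total is 48 + 88 = 136 (inferred, not stated), so the 50% review falls at 68 infants. Halving each stratum gives 24 low-risk and 44 high-risk infants, that is 12 and 22 per arm, or 34 per arm. The test is two-sided at 0.05 without continuity correction, and each infant counts once as event or no event. All event rates are assumed.

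**Large-sample check.** With n_s infants per arm in stratum s, event rate p_s and pooled rate p̄, the null SD of the pooled z is √[Σ n_s p_s(1−p_s) / (n p̄(1−p̄))]. At 5% low and 30% high:
- p̄ = (12×0.05 + 22×0.30)/34 = 7.2/34 = 0.212
- numerator = 12×0.0475 + 22×0.21 = 5.19
- denominator = 34×0.2118×0.7882 = 5.68
- SD = √(5.19/5.68) = 0.956, so nominal size is about 4.0%

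At 5%/10% the same formula gives SD 0.996 and size 4.9%. The direction is right, but the effect is small unless the gap is wide.

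**Exact enumeration of all binomial outcomes.** The pooled test uses z = d / √[2n p̄(1−p̄)], where d is the difference in event counts between arms. The Mantel-Haenszel test sums, over strata, observed minus expected events in one arm (expected = m_s/2) and divides by √Σ m_s(N_s−m_s)/[4(N_s−1)], where m_s is the number of events and N_s the number of infants in the stratum.

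Size:

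| Low / high risk rate | Pooled | Mantel-Haenszel |
|---|---|---|
| 5% / 10% | 5.4% | 5.4% |
| 5% / 20% | 4.9% | 5.1% |
| 5% / 30% | 4.3% | 4.8% |
| 5% / 40% | 3.8% | 5.0% |

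Power, low risk 5% in both arms, harm confined to high-risk infants:

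| High risk, comparison vs harmed arm | Gap between strata, averaged over arms | Pooled | Mantel-Haenszel |
|---|---|---|---|
| 10% vs 35% | 22.5 − 5 = 17.5 points | 45.6% | 46.5% |
| 20% vs 45% | 32.5 − 5 = 27.5 points | 36.5% | 38.8% |
| 30% vs 60% | 45 − 5 = 40 points | 42.0% | 48.8% |

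Harm in both strata:
- 10% vs 20% (low) with 40% vs 65% (high): 39.0% to 43.2%.
- 5% vs 20% (low) with 10% vs 30% (high): 53.4% to 53.0%.
- 10% vs 30% (low) with 20% vs 50% (high): 69.8% to 69.1%.

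Stratifying can therefore cost a fraction of a point when the gap is small.

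**Scale.** By the normal approximation at 34 per arm, the pooled test has about 21% power for 10% vs 20% and 54% for 10% vs 30%. Stratifying leaves these essentially unchanged.

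**The case against.** - **The formula is not visible.** A reader might infer that the test is definitely unstratified. The documents do not establish that: the text is silent and the formula is in a linked source. If the deviate is count-based, (a−b)/√(a+b), with a and b the event totals in the two arms, its size is about 2.0% at 5%/30% and 3.7% at 10%/10%. Most of the conservatism would then come from that variance formula and not from omitting strata. This stands, and it is why the point is conditional.
- **A pooled test is not always conservative.** A reader might infer that any difference between strata costs size and power. At 68 infants the pooled size is 5.4% at both 5%/10% and 5%/15%, above nominal, and the power change is within about one point. This stands.
- **High rates are not documented.** The plan calls aspiration theoretically possible and hypothesises that gastric feeding is well tolerated. Nothing supports 30-40% in high-risk infants. The stratum mean durations, 83.3 and 87.75 h, are close, but they are not adverse-event rates and settle nothing either way.
- **Pooling is not an error.** A simple pooled monitoring test is valid, and conservatism does not add false stops. Daily physician assessment, withdrawal and change of feeding mode also protect infants, and nothing bars the safety coordinator from looking at counts by risk group. All true. These reduce the stakes, but they do not say how the test is to be done.

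**Conclusion.** The point holds in a limited form. The plan stratifies its randomisation and primary model by risk group and mentions no stratum term in the safety test. If that test is a pooled two-proportion z, then under the assumptions above it becomes noticeably conservative once event rates differ between strata by about 25-30 points or more. For harm confined to high-risk infants, stratifying gains between 0.9 points (10% vs 35%) and 6.8 points (30% vs 60%). At small gaps there is nothing to choose between the tests.

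The result rests on an inferred total of 136, a 12/22 mix per arm, a two-sided test and assumed event rates. It does not show that the safety test is invalid, nor that a material loss will occur. This is an optional-to-minor improvement and not a major defect. The low power at about 34 infants per arm is the larger limitation, and it remains.

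**What to change.** In Data and Safety Monitoring, state that the 50% comparison of infants with at least one adverse event is a single Mantel-Haenszel test stratified by risk group, kept at the existing p<0.05. Write the formula in the protocol in place of reliance on the link, and state whether the test is one- or two-sided. Give the reviewer the counts by arm within each risk group alongside the test result.

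The cost is a sentence or two. Risk group is already held in REDCap for randomisation, and no extra tests, staff or patients are needed.
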